6.1.3 Other study parameters

Baseline data: age, gender, social economic status, location and severity of the trauma (1 week after treatment).

6.2 Randomization, blinding and treatment allocation

This is an observational cohort study, so randomization and blinding are not applicable.

6.3 Study procedures

Hospital

Light trauma care (treatment of non-complex fractures and bone dislocations) is generally provided by emergency care doctors, under supervision of (trauma) surgeons. When a radiologist diagnoses a non-complex fracture or dislocation, the emergency care doctors clinically assess the patients, as well as evaluate the X-ray diagnosis. When the emergency care doctor agrees with the diagnosis he composes a treatment plan. When needed, he may assess a trauma surgeon for supervision. The treatment plan is presented to the patient and after approval the emergency care doctor treats the patient. The trauma surgeon provides follow-up consults in his outpatients' clinic. Treatment, follow-up consults, all procedures and management are provided according to the standard of surgical care in the Antonius Hospital Sneek.

General practice

Zorgplein Lemmer is a general practice where regular general medical care is provided by three general practitioners, supported by nurse practitioners, nurses, and doctor's assistants. The Antonius Hospital Sneek equipped this general practice with a regular X-ray facility, which is operated by a radiographer who is employed by the hospital. Digital images are digitally transmitted to in the Antonius Hospital Sneek, where they are assessed by a radiologist. When a non-complex fracture or dislocation is diagnosed, one of the for this purpose well-trained general practitioners is asked to clinically assess the patient, as well as to evaluate the X-ray diagnosis. When the general practitioner agrees with the diagnosis and no contraindications for treatment in the general practice (e.g. severe divergent bone position, suspicion of damage to nerves, vessels or tendons) are indicated, the general practitioner composes a treatment plan according to the treatment protocol. When needed, the general practitioner telephonically assesses a trauma surgeon from the Antonius Hospital Sneek, who is able to assess the X-ray as well. The treatment plan is presented to the patient and after approval the general practitioner treats the patient. This general practitioner also provides follow-up consults in his practice. Treatment, follow-up consults, all procedures and management is provided according to the hospital's standard of care.

Any other treatment not specifically described in this investigation is performed according to the standard of surgical care in the Antonius Hospital Sneek.

Inclusion of participants

The assessment of eligibility will be performed by participating general practitioners near Lemmer, who will approach each potential study patient and inquire about their interest and eligibility in participating in this study. Both the Zorgplein Lemmer as well as the Antonius Hospital Sneek will be informed and trained about the importance of recruiting consecutive patients. If the patient wishes to participate, a legally eligible member of the research team or staff will go through the informed consent process, explaining the purpose of the study, procedures, risk/benefits, alternatives to participation and data protection. Each patient choosing to participate will sign and date an informed consent form. Parents of participants of age 12-17 years old at the date of informed consent must provide a signed and dated written informed consent as well. A copy of the signed informed consent form(s) will be placed into the patient's medical record and the investigator site file and one copy will be handed over to the patient. All patients with written informed consent will be allocated to a unique patient study number. The date of informed consent and the recruitment information is entered in the study database. All patients who commence treatment within the study are considered as enrolled and all enrolled patients should be followed up within the study, except if their study participation is prematurely terminated. All patients recruited in the Zorgplein Lemmer or Antonius Hospital Sneek are automatically allocated to the Zorgplein Lemmer and Antonius Hospital Sneek analysis group, respectively.

6.4 Withdrawal of individual subjects

Patients are allowed to withdrawal at any moment without consequences for their treatment plan or follow-up consultations.

6.5 Follow-up of subjects withdrawn from treatment

Patients are allowed to withdrawal at any moment without consequences for their treatment plan or follow-up consultations.

7. SAFETY REPORTING

7.1 Section 10 WMO event

In accordance to section 10, subsection 1, of the WMO, the investigator will inform the subjects and the reviewing accredited METC if anything occurs, on the basis of which it appears that the disadvantages of participation may be significantly greater than was foreseen in the research proposal. The study will be suspended pending further review by the accredited METC, except insofar as suspension would jeopardize the subjects' health. The investigator will take care that all subjects are kept informed.

8. STATISTICAL ANALYSIS

All statistical tests will be performed blinded for treatment allocation.

8.1 Primary analysis

The primary analysis will be conducted using data from all enrolled patients. The reported patient satisfaction at 12 weeks after treatment will be reported at the patient level along with the 95% CIs according to both treatment groups. In addition, univariable and multivariable regression models will be used whereby the outcome will be the patient satisfaction related to the treatment.

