Study population: 200 patients (≥ 12 years old) with fractures or dislocations which are non-complex such that they can be treated in the primary care setting. This sample size will allow us to demonstrate effect sizes of 0.4 (small to medium) or over with 80% (beta 20%) power using a two-sided alpha of 0.05.

Determinants: demographic factors (age, sex, comorbidity), nature of the trauma, treatment setting (in general practice or in the hospital, distance to treatment center), treatment results (functionality scores, complications, general health, quality of life), time consumption and costs.

Main study parameters/endpoints:

Primary:

- Patient satisfaction (questionnaires after 1, 6, and 12 weeks)

Secondary:

- General health (GHQ questionnaire), age, SES (after 1 week)
- Complications (e.g. secondary dislocation and pain scores; questionnaire after 12 weeks)
- Physical function (questionnaire after 12 weeks)
- Time consumption (questionnaires after 1, 6, and 12 weeks)
- Costs (economic evaluation; questionnaire after 12 weeks).

Nature and extent of the burden and risks associated with participation, benefit and group relatedness:

Since this is an observational study using a limited number of questionnaires in patients who receive regular care, there is no risk associated with participating in this study. The burden for participating patients will very low because they will only be asked to fill in a few questionnaires, which take about one and a half hours in total to fill in.

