4.4 Sample size calculation

The sample size calculation has been performed based on the difference in patient satisfaction. There was no literature available concerning patient satisfaction in trauma care in general practices or hospitals. Therefore, we based our sample size calculation on an estimated effect size. With a significance level of 5%, a power of 80% and equal treatment groups, a sample size of 200 patients (100 per group) was calculated. This sample size will allow us to demonstrate effect sizes of 0.4 (small to medium) or over.

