6. METHODS

6.1 Study parameters/endpoints

6.1.1 Main study parameter/endpoint

Patient satisfaction measured using the Patient Satisfaction Questionnaire Short Form (PSQ-18; 12 weeks after treatment).

Marshall GN Hays RD. The Patient Satisfaction Questionnaire Short-Form (PSQ-18). Santa Monica, CA: RAND, 1994.

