6.1.2 Secondary study parameters/endpoints

1. Patient satisfaction measured using the PSQ-18 (1 and 6 weeks after treatment).

Marshall GN Hays RD. The Patient Satisfaction Questionnaire Short-Form (PSQ-18). Santa Monica, CA: RAND, 1994.

2. Complications of treatment and pain scores (12 weeks after treatment).
3. Physical functioning according to the 12-item World Health Organisation (WHO) Disability Assessment Schedule II (12 weeks after treatment).

*World Health Organization Disability Assessment Schedule II (WHO-DAS II)
WHO, Geneva (2000) www.who.int/icidh/whodas/whodasversions/12int.pdf*

4. Limitations in functions of upper extremities (if applicable) according to the Disabilities of the Arm, Shoulder and Hand (DASH) questionnaire (12 weeks after treatment).

5. General health status according to the 12-item General Health Questionnaire (GHQ-12; 12 weeks after treatment).

Goldberg, D. P. (1972). The Detection of Psychiatric Illness by Questionnaire. Maudsley Monograph No. 21. Oxford University Press: Oxford.

6. Quality of life using the EQ5D questionnaire (12 weeks after treatment).

Euroqol Group (1990) Euroqol—a new facility for the measurement of health-related quality of life. Health Policy 16:199–208

7. Time consumption (waiting time, treatment time, travelling time and distance; 1, 6, and 12 weeks after treatment).

8. Costs (12 weeks after treatment).

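### Section 8.1 promises all enrolled patients but gives no method for those without a 12-week PSQ-18, so non-responders drop out by default, scores already collected at weeks 1 and 6 go unused, and the 80% power assumes almost no loss

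*Combined protocol and SAP*

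**What the plan says.** On the analysis set, section 8.1 says: "The primary analysis will be conducted using data from all enrolled patients". On the outcome it says: "The reported patient satisfaction at 12 weeks after treatment will be reported at the patient level along with the 95% CIs", by treatment group. It then announces univariable and multivariable regression of satisfaction, without naming a visit or any covariates.

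The Summary gives the primary endpoint as "Patient satisfaction (questionnaires after 1, 6, and 12 weeks") and names no instrument. Section 6.1.1 gives "Patient satisfaction measured using the Patient Satisfaction Questionnaire Short Form (PSQ-18; 12 weeks after treatment"). Section 6.1.2 lists as secondary "Patient satisfaction measured using the PSQ-18 (1 and 6 weeks after treatment").

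Loss is foreseen. Section 6.3 says that "all enrolled patients should be followed up within the study, except if their study participation is prematurely terminated". Section 6.4 says: "Patients are allowed to withdrawal at any moment without consequences for their treatment plan or follow-up consultations".

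Section 4.4 states that, with 5% significance, "a power of 80% and equal treatment groups, a sample size of 200 patients (100 per group) was calculated", for effect sizes of 0.4 or more. The Summary adds that the test is two-sided. No allowance for loss is mentioned.

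No section gives a rule for a missing satisfaction score. Section 8.2 repeats the all-enrolled set without a method. The sensitivity techniques in section 8.3 belong to the cost-utility model.

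**The concern.** The stated analysis set and the stated outcome do not fit together without a missing-data method. A patient without a 12-week score contributes nothing to a regression on that score, so the all-enrolled analysis becomes an analysis of responders unless something more is specified.

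The Introduction says that similar results in the two settings may support substitution of this care nationwide, so the estimated difference should not depend on who returned the last questionnaire. The settings are not randomised, and follow-up is given by different providers (section 6.3: the treating general practitioner, or the trauma surgeon's outpatient clinic). Response that differs by setting is therefore plausible, though undocumented. It could create a difference or hide one. Leaving the method open also allows it to be chosen after the data are seen.

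The information that would reduce the problem is already planned, since PSQ-18 is collected at weeks 1 and 6.

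**Working it through.** **Sample size: the plan's own figure.** Inputs from section 4.4 and the Summary: two-sided alpha 0.05, power 80%, equal groups, standardised effect 0.4.

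- Normal approximation: n per group = 2(1.960 + 0.842)²/0.4² = 98.1, so 99 per group and 198 in total.
- Two-sample t-test: 99.08, so 100 per group and 200 in total. The plan's figure is reproduced, with no margin beyond rounding.

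**Effect of loss on an unadjusted t-test.** The loss rates are assumed and equal in both groups. R² is the share of outcome variance that covariates must explain to bring power back to 80%, from detectable effect × √(1 − R²) = 0.4.

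| Loss | Per group with a score | Power for 0.4 | Detectable effect at 80% | R² needed |
|---|---|---|---|---|
| 0% | 100 | 80.4% | 0.398 | none |
| 5% | 95 | 78.3% | 0.409 | 0.04 |
| 10% | 90 | 76.1% | 0.420 | 0.09 |
| 20% | 80 | 71.0% | 0.446 | 0.19 |

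The R² column ignores any cost from covariates that are correlated with setting.

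**Bias of a responders-only comparison.** Everything here is assumed: no true difference, 20% missing in each setting, scores in SD units, and between-visit correlation ρ of 0.5 or 0.7. Less satisfied patients are less likely to answer: P(missing) = expit(a − slope × score), with a set to give 20% overall.

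- Slope 0.5: a = −1.459, so 28% are missing at −1 SD and 12% at +1 SD.
- Slope 1: a = −1.650, so 34% and 7%.

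The responders' mean in that setting is E[Y(1 − P(missing))]/0.80. If loss depends on the 12-week score, this is 0.096 SD (slope 0.5) or 0.173 SD (slope 1) too high. If loss depends on the week-6 score, multiply by ρ: 0.5 × 0.096 = 0.048, 0.7 × 0.096 = 0.067, 0.5 × 0.173 = 0.087, 0.7 × 0.173 = 0.121.

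The bias in the setting difference is the gap between the two settings' errors. If loss in the other setting is completely random, its error is zero. With slopes 1 and 0.5 the gap is 0.173 − 0.096 = 0.077, or 0.039 and 0.054 after multiplying by ρ. With the same mechanism in both settings it is zero.

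The last column comes from large-sample fits that use the week-1 and week-6 scores. Ranges run over ρ, and over both slopes in the one-setting rows.

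| Scenario | Responders only (SD) | Using weeks 1 and 6 (SD) |
|---|---|---|
| Same mechanism in both settings | 0 | 0 |
| Slopes 1 and 0.5, week-6-dependent | 0.04-0.05 | about 0 |
| Slopes 1 and 0.5, 12-week-dependent | 0.08 | 0.04-0.05 |
| One setting only, depends on observed week-6 score | 0.05-0.12 | about 0 |
| One setting only, week-6 form also missing | 0.05-0.12 | 0.02-0.05 |
| One setting only, 12-week-dependent | 0.10-0.17 | 0.04-0.12 |

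**Check at 100 per group** (3,000 simulated studies, 20 imputations, selective loss in one setting, nominal 5%). False-positive rates were 6.3-12.6% for responders only against 4.6-5.3% with imputation when loss depends on week 6, and 9.2-19.9% against 6.2-11.0% when it depends on week 12. With 20% missing at random and a true effect of 0.4, power was 70.2% against 72.3% (ρ = 0.5) and 69.9% against 75.7% (ρ = 0.7). The gain is therefore mainly in bias, and only modestly in power.

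**The case against.** The strongest reply is that the bias is hypothetical. The documents give no response rate, mechanism or correlation, and the largest figures need selective loss in one setting, random loss in the other, a steep slope and dependence on the unobserved score. This stands as a limit on the size. In that worst case, using the earlier scores still leaves 0.08-0.12 SD. It does not remove the gap, because the absence of a rule does not depend on the loss rate.

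A second reply is that the regression sentence in section 8.1 names no visit, so a longitudinal model is not excluded. That is true, and it is why responders-only is an inference. But no such model is stated, and the reporting sentence is tied to 12 weeks. A reader might infer that the plan deliberately chose a complete-case analysis; the text does not say so.

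A third reply concerns power: covariates in the multivariable model could recover some or all of the loss. This also stands, and makes power the secondary part of the point. A reader might infer that 200 is miscalculated or that the study will be underpowered. Neither is supported: 200 is correct for its inputs, and the power actually reached depends on a response rate and covariates that the documents do not give.

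Lastly, imputation is only one choice. A repeated-measures model over the three visits uses the same scores and would serve equally well.

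**Conclusion.** The point holds. Section 8.1 cannot deliver its own analysis set as written: on the natural reading, patients without a 12-week score drop out and their week-1 and week-6 scores are not used. The Summary and section 6.1.1 disagree on the primary time point, and the gap exists on either reading. The stated 80% power for 0.4 holds only if essentially all 200 patients give a 12-week score, in an unadjusted test.

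The size is conditional. At an assumed 20% loss per setting with no true difference, responders-only bias runs from zero (same mechanism in both settings), through 0.04-0.08 SD (slopes 1 and 0.5), to 0.05-0.17 SD (selective loss in one setting only). Using the earlier scores brings the one-setting bias to about zero when loss depends on an observed week-6 score, but leaves 0.04-0.12 SD when it depends on the unobserved 12-week score. A reader might infer that the result will be biased, or that imputation would cure it; the documents support neither. The change should be made because the gap is certain and closing it is cheap.

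**What to change.** 1. Name the same primary time point in the Summary, section 6.1.1 and section 8.1 (section 6.1.1 gives 12 weeks).
2. In section 8.1, keep all enrolled patients and estimate the 12-week setting difference with a method that uses the week-1 and week-6 PSQ-18. Either use multiple imputation from setting, both earlier scores and pre-treatment characteristics (age, gender, socioeconomic status, location and severity of the trauma), or a repeated-measures model over weeks 1, 6 and 12 with setting-by-visit terms. Do not rely on the 12-week predictors listed in section 8.2 (complications, pain, physical functioning, EQ-5D) for the imputation, because they are likely to be missing together with the outcome.
3. Report by setting the 12-week response and the number with no PSQ-18 at any visit. Section 6.1.3 collects baseline data 1 week after treatment, so these patients may have only their setting recorded and add little or no information. Say so.
4. Add one sensitivity analysis that shifts the imputed or predicted 12-week scores in one setting, for example by 0.25 and 0.5 SD. With 20% missing, these move that setting's mean by 0.20 × 0.25 = 0.05 SD and 0.20 × 0.5 = 0.10 SD. Read it both for a false difference and for a masked one, since the conclusion of interest is similarity.
5. In section 4.4 and the Summary, state that 80% power for 0.4 assumes 100 patients per group with a 12-week score in an unadjusted test. Give the detectable effect at assumed response rates (0.42 at 90%, 0.45 at 80%), without enrolling more.

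The cost is wording, one extra analysis step with a shifted re-run, and a slightly less favourable stated figure. Some bias remains if loss depends on the unobserved score.

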8.2 Secondary analyses

Secondary analyses will be conducted using data from all enrolled patients. Initially, univariable statistical tests (eg, χ^2 test or Fisher's exact test for categorical variables; t test or Wilcoxon rank-sum test for continuous variables) will be used to evaluate differences in outcome scores between the two treatment groups. Subsequently, data will be analyzed using multivariable regression models to estimate differences in mean patient satisfaction scores using possible predictors (eg, complications, pain scores, physical functioning, EQ-5D, time consumption) between both treatment groups.

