8.3 Cost-effectiveness

The proposed cost–utility analysis will use decision modeling and sensitivity analysis techniques to ensure the robustness of the study's conclusions. Cost-effectiveness will be assessed using the incremental cost-effectiveness ratio, which is determined by calculating the difference in costs divided by the difference in QALYs between both treatment groups.

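### Secondary outcomes other than satisfaction are compared between two non-randomised settings with univariable tests only, so these comparisons are open to confounding

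*Combined protocol and SAP*

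**What the plan says.** Section 8.2 has two steps. First, chi-square, Fisher, t or Wilcoxon tests "will be used to evaluate differences in outcome scores between the two treatment groups". Then "data will be analyzed using multivariable regression models to estimate differences in mean patient satisfaction scores using possible predictors"; the examples given of those predictors are complications, pain, physical functioning, EQ-5D and time. Section 8.1 also plans univariable and multivariable regression, again with satisfaction as the outcome.

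Section 8.3 describes a cost-utility analysis with decision modelling and sensitivity analysis. Its cost-effectiveness ratio is obtained by "calculating the difference in costs divided by the difference in QALYs between both treatment groups". It does not say how those two differences are estimated.

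On design, 6.2 states: "This is an observational cohort study, so randomization and blinding are not applicable". Under 6.3, patients recruited at each site "are automatically allocated to the Zorgplein Lemmer and Antonius Hospital Sneek analysis group, respectively". Section 6.1.3 lists age, sex, socioeconomic status, injury location and injury severity as baseline data, recorded at 1 week, but no section gives them a role in adjustment. Section 4.2, criterion 1, requires every participant to have a non-complex injury that primary care can treat under the treatment protocol.

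**The concern.** When setting follows from where a patient presents, the two groups can differ in ways that also affect recovery. A univariable test cannot separate such differences from an effect of setting. Regression on measured baseline variables is the usual protection, and the plan provides it only for satisfaction. The function and quality-of-life scores (WHO-DAS II, DASH, EQ-5D) are listed in 6.1.2 only at 12 weeks, so no pre-treatment score could absorb a group difference either.

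These outcomes matter for the study's message. The Summary counts functionality, complications, general health and quality of life as treatment results, and the Summary and section 1 say that results similar to those of the nearby hospitals may support substitution nationwide. If the practice happened to receive the more favourable mix, an unadjusted comparison could show similar results when the practice does worse. With the opposite mix it could show a deficit that does not exist.

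**Working it through.** **Is there an adjusted analysis for any outcome other than satisfaction?**

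| Outcome | Planned comparison of settings | Adjusted model with this as outcome |
|---|---|---|
| Satisfaction (PSQ-18) | 8.1 and 8.2 | Multivariable regression planned |
| Complications, pain, WHO-DAS II, DASH, GHQ-12, EQ-5D, time | Univariable tests, 8.2 | None stated |
| Costs, QALYs | Differences entering the ratio in 8.3 | Adjustment not stated |

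No section plans matching, stratification or a propensity method.

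**The plan's own figure.** Section 4.4 gives 100 per group for an effect of 0.4 SD, with 5% significance and 80% power; the Summary states that alpha is two-sided. The normal approximation is n = 2 × (1.960 + 0.842)² / 0.4² = 98.1, so 99 per group, or 198 in total. Power at 100 per group is 80.7% (80.4% with the t distribution). The stated 200 reproduces and is not affected by this point.

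**Illustration of size.** From the plan: 100 per group, two-sided 5% test. Assumed, because the documents give neither: the difference between groups in the share of more severe injuries, and the effect of severity on a 12-week score.

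- Bias = imbalance × effect. Low case: 0.20 × 0.5 SD = 0.10 SD. High case: 0.30 × 0.8 SD = 0.24 SD.
- Standard error of the difference = √(2/100) = 0.141 SD.
- False-positive rate with no true setting effect = 1 − Φ(1.96 − bias/SE) + Φ(−1.96 − bias/SE).

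| Bias (SD) | Bias/SE | False-positive rate | Share of 0.4 SD |
|---|---|---|---|
| 0 | 0 | 5% | 0% |
| 0.10 | 0.71 | 10.9% | 25% |
| 0.24 | 1.70 | 39.6% | 60% |

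**Check with a continuous confounder.** Assume that case mix differs by 0.2 to 0.5 SD, with outcome slopes of 0.3 to 0.5 SD per SD. The bias runs from 0.2 × 0.3 = 0.06 SD to 0.5 × 0.5 = 0.25 SD, and the false-positive rate from 7.1% to 42.4%. In three scenarios simulated 5,000 times each, the unadjusted test rejected in 7.0%, 17.5% and 42.0% of runs. Adjusting for the measured confounder gave 5.0%, 4.8% and 4.7%.

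These figures apply to a continuous score completed by 100 patients per group. They do not describe complications (binary), costs or times (likely skewed), or DASH, which only patients with upper-extremity injuries complete.

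**The case against.** The strongest reply is that the design already controls case mix. A reader might infer a severity imbalance from 6.3, where a patient stays with the general practitioner only if "no contraindications for treatment in the general practice (e.g. severe divergent bone position, suspicion of damage to nerves, vessels or tendons) are indicated", while the hospital pathway lists no such step. But criterion 1 in 4.2 applies to all participants, so hospital patients with those contraindications should be ineligible too. Section 6.3 also has general practitioners near Lemmer assess eligibility, and trains both sites on consecutive recruitment. This reply largely stands. The documents do not show that case mix will differ in severity, or that the comparisons are in fact biased. What remains possible is a difference in age, sex, socioeconomic status, injury location, or severity within the eligible range.

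Second, these comparisons are not stated objectives: section 2 studies the other factors as determinants of satisfaction. That lowers the weight of the point but does not remove it, because 8.2 expressly plans to test these outcomes between settings and the rationale links similar results to substitution.

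Third, a reader might take 8.3 to plan raw cost and QALY differences. It does not say so. It plans decision modelling and leaves the estimation of the inputs unstated, which is a gap in specification.

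Fourth, travel time and distance depend on residence and site. Confounding by severity is not a convincing mechanism for them.

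**Conclusion.** The point holds as a gap in the analysis plan. Every planned multivariable model has satisfaction as its outcome, so the other patient outcomes have only univariable comparisons between non-randomised settings, and 8.3 is silent on adjustment. These comparisons are open to confounding. The documents do not support saying that they are biased, or in which direction.

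The range of about 11% to 40% rests wholly on an assumed bias of 0.10 to 0.24 SD. Criterion 1 makes a large severity imbalance less likely, and at zero imbalance the test keeps its 5% level. The primary endpoint has a multivariable model, and the sample size stands. The plan should be changed here, but the point does not undermine the primary analysis.

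**What to change.** In 8.2, for each patient-outcome measure in 6.1.2, make the reported result the setting coefficient with 95% CI from a regression adjusted for the 6.1.3 variables: age, sex, socioeconomic status, injury location and severity. Add comorbidity if it is collected, since the Summary lists it among the demographic determinants but 6.1.3 does not. Because 6.1.3 records these data 1 week after treatment, state that severity means severity at presentation.

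- Use linear models for scores, a short covariate list or penalised logistic regression for complications, and models suited to skew for waiting time, treatment time and costs.
- Do not adjust for complications, pain or function as confounders; they arise after treatment.
- Keep the univariable tests as description, and leave travel time and distance descriptive.
- In 8.3, state that the cost and QALY differences entering the model are estimated with the same adjustment.

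The cost is revised wording and a few extra models, with no new data beyond comorbidity if it is not yet collected. Adjustment covers measured confounders only, and the report should say so.
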